1.2 TACE Toxicity

Complication rates following TACE are high (25-45%) with the majority being reversible elevations of hepatic transaminases and serum bilirubin without an impact on long-term prognosis, however, for a small proportion of patients, irreversible hepatic decompensation occurs (15). TACE-related irreversible hepatic decompensation is described as significant and acute elevation of liver function tests, evidence of new ascites, new encephalopathy, or worsening of either. These serious complications, frequently accompanied by deterioration in clinical status, may lead to the requirement of urgent liver transplantation in eligible patients, ineligibility for and/or risk of increased toxicity from systemic therapy with sorafenib or investigational systemic therapies for HCC, or death (16). Rates of complications following conventional TACE performed for patients with marginal hepatic reserve or portal vein thrombosis have been described (16-23).

We have recently completed a retrospective record review of 252 patients with HCC and hepatic dysfunction who underwent 446 cTACE procedures at our institution between 2005 and 2009 (24). Patients were eligible for inclusion if they had one of the following criteria: pre-TACE

bilirubin ≥ 2 mg/dL, aspartate aminotransferase (AST) or alanine aminotransferase (ALT) > 5 times upper normal limit, international normalized ratio (INR) > 1.5 , creatinine > 1.2 mg/dL, platelet count $\leq 60,000/\mu\text{L}$, Model for End-Stage Liver Disease (MELD) score > 15 , Childs-Pugh class B or C, ascites, or portal venous thrombus. Hepatotoxicity was defined as one of the following: new or worsening ascites, encephalopathy, or NCI Common Terminology Criteria for Adverse Events grade 3 or 4 toxicity of bilirubin, AST, ALT, creatinine or INR. Rate and risk factors for persistent hepatotoxicity were determined using generalized estimating equation analysis.

Reversible hepatotoxicity developed after 90 TACE procedures (20%) in 78 patients (31%). Reversible abnormalities resolved in under 30 days after 63 procedures, in 1-3 months after 19 procedures, and in 3-6 months after 6 procedures. Irreversible hepatotoxicity developed after 41 procedures (9%) in 37 patients (15%). Six patients (2%) received urgent liver transplants, and five (2%) died within 30 days of TACE. Patients at increased risk for procedure-related mortality or urgent need for a liver transplant had baseline elevated serum bilirubin ($p < 0.0001$), elevated INR ($p < 0.0001$), hypoalbuminemia ($p = 0.002$), thrombocytopenia ($p = 0.011$), elevated serum creatinine ($p < 0.0001$), large ascites ($p = 0.0002$), encephalopathy ($p = 0.0002$), or MELD > 15 ($p = 0.0005$).

PRECISION V trial (14) showed that DEB-TACE was better tolerated than cTACE and led to better radiographic responses in patients with more advanced liver disease than cTACE. On the basis of this observation, DEB-TACE may, in fact be the preferred modality for treating patients with hepatic dysfunction. All studies performed on safety of DEB-TACE to date included patients with serum bilirubin < 3 mg/dL, and AST and ALT levels under 5X upper normal limit (14, 26-52). Patients with baseline liver dysfunction at bilirubin and transaminase levels above those included in trials are routinely treated in clinical practice. However, there have been no published studies to date to support safety and efficacy of DEB-TACE in patients with marginal hepatic reserve. A total of 37 patients with hepatic dysfunction (who met the inclusion criteria proposed for this study) have been treated between at UCSF between 2011 and 2013. Their records were retrospectively reviewed. Preliminary results on adverse events following DEB-TACE are summarized in Table 1. No treatment-related deaths and no events hepatic decompensation requiring an urgent liver transplant were encountered in this patient cohort.

Table 1. Severe hepatic and renal adverse events in 37 patients with marginal hepatic reserve who underwent DEB-TACE at UCSF.

Toxicity	Bilirubin N (%)	AST N (%)	ALT N (%)	INR N (%)	Creatinine N (%)
Reversible* grade 3	9 (24)	5 (14)	1 (2.7)	0 (0)	0 (0)
Reversible* grade 4	1 (2.7)	1 (2.7)	0 (0)	N/A	0 (0)
Irreversible** grade 3	0 (0)	0 (0)	0 (0)	0 (0)	0 (0)
Irreversible** grade 4	0 (0)	0 (0)	0 (0)	N/A	0 (0)

*Abnormality returned to baseline within 6 weeks of DEB-TACE

**Abnormality persisted for at least 6 weeks following DEB-TACE

1.6 Rationale

TACE is frequently offered to patients with hepatic dysfunction with the purpose of diminishing hepatic tumor burden while patients await transplantation. Without this therapeutic measure, disease may progress beyond UNOS T2 criteria required for organ allocation. PRECISION V randomized controlled trial has suggested that DEB-TACE may be associated with fewer adverse events than conventional TACE. Therefore, the purpose of this study is to determine whether DEB-TACE can be used safely and effectively to treat patients with liver-only HCC and hepatic dysfunction.

2.0 OBJECTIVES

Primary Objective

- To determine the safety of DEB-TACE in patients with HCC confined to liver who are being considered for liver transplantation
- To determine the response rate to DEB-TACE by conventional and modified Response Evaluation Criteria in Solid Tumors (RECIST version 1.1, mRECIST [22]) for treated lesions in patients with liver-only HCC who are being considered for liver transplantation.

Secondary Objectives

- To measure overall radiographic response (by RECIST v1.1 and mRECIST) 6 months after the date of the first planned DEB-TACE procedure. To measure time to untreatable progression (TTUP). TTUP is defined as time to disease progression untreatable by liver-directed percutaneous or surgical methods.
- To measure median time to progression (TTP)
- To measure hepatic progression free survival (HPFS)
- To measure progression free survival (PFS)
- To measure overall survival (OS).
- To determine the proportion of patients who remain active on the wait list for a liver transplant and eventually are transplanted.
- To determine the proportion of patients who are inactivated or drop out from the wait list for any reason but transplantation.
- To determine the proportions of patients who are successfully down-staged and achieve active waitlist status and eventually are transplanted.
- To measure proportion with alpha-fetoprotein (AFP) response with $\geq 50\%$ decline from baseline (in patients with baseline level ≥ 20) post DEB-TACE and test for association with hepatic and overall response rate, PFS, and OS.
- To determine whether changes in cardiac function occur as a result of DEB-TACE with doxorubicin
- ***To obtain pharmacokinetic data for doxorubicin administered as a part of DEB-TACE procedures***

Exploratory/Other Objectives

- To describe treatment response by histopathology at the time of liver transplantation (in the subgroup of patients who undergo LT).

3.0 STUDY DESIGN

This is a prospective open-label two-stage phase II clinical trial to evaluate the safety and efficacy of DEB-TACE in patients with liver-only HCC and hepatic dysfunction who are being considered for a liver transplant. Seventeen patients will be enrolled during the first stage of the study for efficacy. Subsequently, 34 patients will be enrolled into the second stage of the study. Prior surgical resection or liver-directed therapy will be allowed. Patients will be followed for one year following DEB-TACE. This study will take up to five years to complete.

3.1 Single DEB-TACE procedure algorithm

Patients who meet the eligibility criteria in Section 4.0 and present with HCC confined to one liver segment supplied entirely by one segmental branch of the hepatic artery the right or the left hepatic artery will be offered a single DEB-TACE treatment intended to target the entire tumor vasculature. The following algorithm will be adhered to for patients with disease confined to one liver lobe or segment:

One to sixty days prior to treatment, patients will undergo imaging of the abdomen with contrast-enhanced CT or MRI. Within one to six days prior to DEB-TACE, laboratory tests including CBC, BUN, creatinine, coagulation panel, liver function tests, and serum alpha-fetoprotein level (AFP) will be performed. A history and physical examination will be performed within six days prior to and the day of DEB-TACE (Table 1).

For the purposes of DEB-TACE procedure, hepatic angiogram will be performed in the standard fashion via a common femoral artery approach. Coaxial microcatheter will be used for selective catheterization of a segmental or subsegmental hepatic artery branch. Up to two 2 ml vials of 100-300 μ m LC-BeadsTM impregnated per manufacturer-supplied protocol with 25mg of doxorubicin per ml of beads will be administered into the catheterized hepatic artery. Procedure will be stopped when arterial flow approaches stasis and/or when the entire DEB dose has been administered.

Patients will be on bed rest for approximately 4-8 hours following removal of the femoral artery catheter. Per institutional standard, they will be admitted for planned overnight observation to the hospital and discharged once determined to be in stable condition. Management after each DEB-TACE procedure will be according to institutional standard of care.

Patient follow-up is summarized in section 8.4 and section 8.4.1.

3.2 Treatment Algorithm for Multiple DEB-TACE procedures

Patients who meet the eligibility criteria in Section 4.0 with a lesion or lesions supplied by more than one segmental hepatic artery branch will be considered for up to four sequential DEB-TACE procedures intended to target the entire tumor vascular supply in a step-wise fashion. The number of procedures will be based on the number, location, and size of the lesions as well as on the hepatic arterial anatomy up to a maximum of 4 DEB-TACE procedures. This information will be obtained from the pre-procedure cross-sectional imaging (CT or MRI), hepatic artery angiography, and C-arm CT (when applicable).

Sequential DEB-TACE may be offered in the following settings:

- A. Multifocal HCC (UNOS T2 or T3 disease; no radiographic evidence of macrovascular invasion or extracapsular extension)
- B. Single HCC greater than 3 cm (UNOS T2 or T3 disease without radiographic evidence of macrovascular invasion or extracapsular extension).
- C. More than 1 segmental feeding hepatic artery branch to a lesion of any size.

Pre-procedure evaluation will be the same as for patients undergoing one DEB-TACE procedure (Table 2). For each DEB-TACE procedure, up to two 2 ml vials of 100-300 μ m LC-Beads[®] impregnated per manufacturer-supplied protocol with 25mg of doxorubicin per ml of beads will be administered into the catheterized hepatic artery. Procedure will be stopped when arterial flow approaches stasis and/or when the entire DEB dose has been administered.

Sequential DEB-TACE procedures will be performed approximately 1 month apart. Longer intervals between the procedures may be necessary. The timing of DEB-TACE will be determined by the treating interventional radiologist and hepatologist or medical oncologist. The number of procedures (up to 4 total) will be based on the number, location, and size of the lesions as well as on the hepatic arterial supply to the lesions. This information will be obtained from the pre-procedure cross-sectional imaging (CT or MRI) and hepatic artery angiography. This step-wise approach is intended to target the entire tumor vascular supply in a step-wise fashion prior to assessing response to therapy.

The maximum administered doxorubicin dose per DEB-TACE procedure (session) will be 100mg (50 mg per each 2 ml vial of 100-300 μ m LC beads). The maximum administered dose as a result of four DEB-TACE procedures will be 400 mg.

Post-procedure follow-up for the first month after DEB-TACE will be as outlined in Table 2. Additional treatment will be offered if the following criteria are met:

1. Patient is willing to undergo additional DEB-TACE treatment.
2. Patient meets all of the inclusion criteria and none of the exclusion criteria (see sections 4.2 and 4.3 below) at the time of 20-day follow-up.

Patient follow-up is summarized in section 8.4 and section 8.4.2.

4.0 ELIGIBILITY CRITERIA

4.1 Subject Population

Patients with liver-only HCC UNOS stage T1, T2, or T3 being considered for liver transplantation at UCSF will be eligible. Patients who have undergone prior resection, chemoembolization, radioembolization, bland embolization, ablative therapy or systemic therapy will be eligible to participate in the study.

Treatment with DEB-TACE will be offered to patients being considered for liver transplantation under one of the following protocols:

1. Milan criteria: One lesion less than 5 cm or up to 3 lesions each less than 3 cm.
2. UCSF Downstaging criteria: One lesion less than 8 cm or 2-3 lesions each less than 5 cm with sum of maximum dimensions less than 8 cm, or 4-5 lesions each less than 3 cm with sum of maximum dimensions less than 8 cm.
3. UCSF All-Comers criteria: UNOS stage T3 disease beyond UCSF Downstaging Criteria.

4.2 Inclusion Criteria

1. Adult male or female patients, age 18 years of age or older
2. Diagnosis of liver-only HCC based on European Association for the Study of the Liver (EASL) criteria (radiographic lesion appearance on contrast-enhanced CT or MRI, i.e. enhancement on early arterial phase, washout on portal venous phase with or without associated elevation of serum AFP level $>200\text{U/ml}$) or histologic confirmation of HCC diagnosis, whichever is applicable.
3. UNOS stage T1, T2, or T3 disease.
4. Candidates for liver transplantation (listed or screened) according to one of the following criteria:
 - a. Milan criteria (one lesion $< 5\text{cm}$ or 3 or fewer lesions each $< 3\text{cm}$),
 - b. UCSF Downstaging criteria (one lesion less than 8 cm or 2-3 lesions each less than 5 cm with sum of maximum dimensions less than 8 cm, or 4-5 lesions each less than 3 cm with sum of maximum dimensions less than 8 cm)
 - c. UCSF All-Comers criteria (UNOS stage T3 disease beyond UCSF Downstaging Criteria).
5. At least one measurable site of disease in the liver according to RECIST version 1.1 and mRECIST criteria.
6. **At least one** of the following clinical, laboratory, or imaging parameters:
 - a. Mild or moderate ascites
 - b. Serum bilirubin $\geq 3\text{ mg/dl}$ but less than 6 mg/dl
 - c. Aspartate aminotransferase (AST) > 5 times upper limit of normal (ULN) but ≤ 10 times ULN
 - d. Alanine aminotransferase (ALT) > 5 times upper limit of normal (ULN) but ≤ 10 times ULN
 - e. International normalized ratio for prothrombin time (INR) >1.5 but ≤ 2.5
 - f. Bland portal vein thrombosis (branch or main)
 - g. Functioning transjugular intrahepatic portosystemic shunt (TIPS) or surgical portosystemic shunt
7. ECOG performance status of 0, 1, or 2.
8. Ability to give written informed consent.

Patients should meet the above study entry criteria at study enrollment as well as prior to undergoing each subsequent DEB-TACE procedure.

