4.3 Exclusion Criteria

1. Liver-directed therapy (chemoembolization, radioembolization, bland embolization, ablative therapy) within 4 weeks of DEB-TACE.
2. Previous liver transplantation.

3. Serum bilirubin \geq 6 mg/dl
4. AST > 10 times upper normal limit
5. ALT > 10 times upper normal limit

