8.0 EVALUATIONS AND PROCEDURES

Table 2 Schedule of Events: Single Deb-TACE

	Pre-treatment		DEB-TACE	Post Treatment Evaluation							
	Screening Evaluation	-60 to 0 days		-6 ± 6d	Day 0	1 ± 0d	7 ± 4d	30 ± 7d	90 ± 14d	180 ± 14d	270 ± 14d
Clinical/Administrative Activities											
Informed Consent	X										
Demographics	X										
Medical History	X										
Physical Examination	X	X									
ECOG Performance Status (See Appendix 1)	X	X				X	X	X	X	X	
Child Pugh Turcotte Score (See Appendix 2)	X					X	X	X	X	X	
MELD Score (See Appendix 3)	X					X	X	X	X	X	
Interim History + Physical Exam					X*	X	X	X	X	X	
Evaluation of Response						X	X	X	X	X	
Laboratory Tests											
CBC, Coagulation Panel, BUN, Creatinine, Liver Function Tests	X	X			X	X	X	X	X	X	
Alpha-fetoprotein		X				X	X	X	X	X	
Imaging Studies											
Contrast-Enhanced CT or MRI of the abdomen	X					X	X	X	X	X	
CT chest with and/or without contrast	X						X	X	X	X	
Cardiac Function Assessment											
Echocardiogram	X&						X&				
DEB-TACE Procedure											
DEB-TACE			X								
Pharmacokinetics Evaluation											
Pharmacokinetics sample acquisition**			X	X	X						

Abbreviation: d = days

* May be substituted by telephone follow-up by interventional radiology nurse practitioner for patients who are non-local study participants.

& Cardiac function will be assessed via echocardiogram at baseline and one month following last planned DEB-TACE.

** See plan for pharmacokinetic data acquisition in Sections 8.1 and 8.4

Table 3 Schedule of Events: Multiple DEB-TACE procedures*

	Pre-treatment Evaluation	DEB-TACE 1	Evaluation TACE 1	DEB-TACE 2	Evaluation TACE 2	DEB-TACE 3	Post Treatment Evaluation TACE 3	DEB-TACE 4**				
	-60 to 0 days	-6 ± 6d	Day 0	1d	7 ± 4d	30 +30d (Reset to d0)	1d	7 ± 4d	30 +30d (Reset to d0)	1	7 ± 4d	30 +30d (Reset to d0)
Clinical / Administrative Activities												
Informed Consent	X											
Demographics	X											
Medical History	X					X			X			X
Physical Examination	X	X										
ECOG Performance Status	X	X				X			X			X
Child Pugh Turcotte Score (See Appendix 2)	X											
MELD Score (See Appendix 3)	X					X			X			X
Interim History + Physical Exam					X	X		X	X		X	X
Laboratory Tests												
CBC, Coagulation Panel, BUN, Creatinine, Liver Function Tests	X	X		X	X	X	X	X	X	X	X	X
Alpha-fetoprotein		X										

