Imaging Studies												
Contrast-Enhanced CT or MRI of the abdomen	X											
CT chest with and/or without contrast	X											
Cardiac Function Assessment												
Echocardiogram	X ^{&}					X ^{&}			X ^{&}			X ^{&}
DEB-TACE Procedure												
DEB-TACE**			X			X**			X**			X**
Pharmacokinetics Evaluation												
Pharmacokinetics data acquisition***			X	X	X							

Abbreviation: d = days

* See Table 2 for post-treatment evaluation after DEB-TACE 4. DEB-TACE 3 and 4 are optional for patients with disease extent limited to two liver segments. Patients may proceed to evaluation of response and long-term follow-up after fewer than 4 DEB-TACE treatments at the investigator's discretion.

& Cardiac function will be assessed via echocardiogram at baseline and one month following last planned DEB-TACE.

** Up to 4 DEB-TACE procedures may be performed at approximately 1 month intervals depending upon initial size, number, vascular supply of lesion(s) and interval treatment response on imaging.

*** See plan for pharmacokinetic data acquisition in Sections 8.1 and 8.4

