8.3 Multiple DEB-TACE Procedures Targeting Different Vascular Territories

Sequential DEB-TACE procedures may be offered in the following settings:

- A. Multifocal HCC (UNOS T2 or T3 disease; no radiographic evidence of macrovascular invasion or extracapsular extension).
- B. Single HCC greater than 3 cm (UNOS T2 or T3 disease without radiographic evidence of macrovascular invasion or extracapsular extension).
- C. More than 1 segmental feeding hepatic artery branch to a lesion of any size.

Patients with lesions that meet at least one of these criteria will be considered for up to four DEB-TACE procedures that will be performed approximately 1 month apart. Longer intervals between the procedures may be necessary in order to allow patients to regain pre-TACE liver function and performance status. Intervals between DEB-TACE procedures up to 90 days will be allowed. The timing of DEB-TACE will be determined by the treating interventional radiologist and hepatologist or medical oncologist. The number of procedures (up to 4 total) will be based on the number, location, and size of the lesions as well as on the hepatic arterial supply to the lesions. This information will be obtained from the pre-procedure cross-sectional imaging (CT or MRI) and hepatic artery angiography. This step-wise approach is intended to target the entire tumor vascular supply in a step-wise fashion prior to assessing response to therapy (Table 2).

The maximum administered doxorubicin dose per DEB-TACE procedure will be 100mg (50 mg per each 2 ml vial). The maximum administered dose as a result of four DEB-TACE procedures will be 400 mg.

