Approximately one month after last planned DEB-TACE procedure, patients will undergo repeat cross-sectional imaging with multi-phase contrast-enhanced CT or MRI of the abdomen. First follow-up imaging study will be obtained no more than 6 months following the first DEB-TACE procedure. Subsequent imaging will be performed at approximately 3 month-intervals until 360 days following DEB-TACE. Standard clinical practices will be adhered to during the follow-up period.

Response to treatment will be assessed according to RECIST version 1.1 and mRECIST criteria (see section 9.2).

Patients will be removed from study and follow-up assessments will stop prior to 360 days following DEB-TACE if a patient:

- a) requires > 4 DEB-TACE procedures
- b) requires another anti-cancer treatment modality such as ablation, surgery, or conventional TACE

- c) receives a liver transplant
- d) develops untreatable intrahepatic or extrahepatic disease progression
- e) experiences unacceptable toxicity (see section 10.1). All serious adverse events will be followed until the SAE has been resolved.

Pathology report describing the extent of HCC in the liver explant will be reviewed for the subset of patients who undergo LT.

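### Inclusion 6 (at least one sign of liver dysfunction) is re-applied before every repeat session, so as written a patient whose qualifying items have all cleared cannot have the next planned DEB-TACE while that lasts

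*Combined protocol and SAP*

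**What the plan says.** Two places set the rule for sessions 2 to 4. Section 4.2, after listing eight inclusion criteria, states: "Patients should meet the above study entry criteria at study enrollment as well as prior to undergoing each subsequent DEB-TACE procedure". Section 3.2 offers further treatment if the patient is willing and if "Patient meets all of the inclusion criteria and none of the exclusion criteria", judged "at the time of 20-day follow-up".

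Inclusion 6 differs in kind from the other entry criteria because it asks for an abnormality to be present. Any one of seven items is enough: mild or moderate ascites; bilirubin from 3 to below 6 mg/dl; AST or ALT above 5 and up to 10 times the upper limit of normal (ULN); INR above 1.5 and up to 2.5; bland portal vein thrombosis; or a functioning portosystemic shunt. It need not be the item met at entry.

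Other sections allow some flexibility:

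- Section 8.3: "Intervals between DEB-TACE procedures up to 90 days will be allowed". Its stated reason for longer gaps is recovery of liver function and performance status to their level before treatment.
- Section 8.4.2: candidacy for a repeat session rests on laboratory and clinical review at day 7±4 and on the day of the session. The treating physicians may delay or cancel. Also, "First follow-up imaging study will be obtained no more than 6 months following the first DEB-TACE procedure".
- Notes to Table 3: "Patients may proceed to evaluation of response and long-term follow-up after fewer than 4 DEB-TACE treatments", at the investigator's discretion.

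None of these allows a session to go ahead with an entry criterion unmet.

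**The concern.** A re-treatment check normally asks whether the patient is still well enough. Re-applying inclusion 6 also asks whether the patient is still unwell enough. A patient whose qualifying items have all cleared then waits, while one near the upper limits proceeds.

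Section 3.2 plans sequential sessions to cover the whole tumour blood supply before response is assessed. A block under inclusion 6 delays that. If it outlasts the time limits in 8.3 and 8.4.2, planned tumour stays untreated. That tumour falls outside the primary endpoint, which counts treated lesions, but it enters the 6-month overall response in section 12.3, which counts all measurable liver lesions. If staff treat anyway, the session departs from the plain wording of 3.2 and 4.2.

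**Working it through.** **1. The plan's own design figures.** Exact binomial calculation with 17 + 34 patients, stopping at 4 or fewer of 17 responses and negative at 14 or fewer of 51, gives type I error 0.0487 at a 20% response rate and power 0.854 at 40%. The chance of stopping after stage 1 is 0.758 and 0.126. The plan states 5%, 85%, 76% and 13%. These reproduce, and nothing below alters them.

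**2. What the re-check adds beyond the exclusions.**

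| Inclusion 6 item | Upper limit in item 6 | Upper limit in section 4.3 | Added by the re-check |
|---|---|---|---|
| Bilirubin | below 6 mg/dl | exclusion 3, 6 mg/dl or more | lower bound only |
| AST | 10 × ULN | exclusion 4, "AST > 10 times upper normal limit" | lower bound only |
| ALT | 10 × ULN | exclusion 5, above 10 × ULN | lower bound only |
| INR | 2.5 | exclusion 6, above 2.5 | lower bound only |
| Ascites | moderate | none | lower bound and a partial upper limit |
| Bland thrombosis, shunt | none | none | presence only |

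The ascites limit is partial because a patient with severe ascites still satisfies inclusion 6 through any other item.

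**3. How many patients meet the re-check.** The Abstract expects most patients to need one session. Most of 51 is at least 26, so at most 51 − 26 = 25 have a repeat session. The documents give no rate at which all seven items clear, so the number blocked cannot be calculated.

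**4. When a delay becomes a lost session.**

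- One interval: sessions are about 30 days apart and 8.3 allows 90, so slack is 90 − 30 = 60 days. Table 3's window for the next session ends at day 30 + 30 = 60, which would leave only 60 − 30 = 30 days.
- Whole course of four: sessions fall on about days 0, 30, 60 and 90. The response scan follows the last by about 30 days and is due by about day 180, so the last session must be by about day 150. Total slack is 150 − 90 = 60 days.

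**5. Illustration for one patient.** Assumptions, none from the documents: bilirubin is the only item, its true mean does not change, visit-to-visit variation is normal with coefficient of variation (CV) 10%, 15% or 20%, and checks are independent. The chance of reading below 3.0 is Φ((3.0 − m)/(CV × m)). For m = 3.2 and CV 10% this is Φ(−0.2/0.32) = Φ(−0.625) = 0.266. Two checks in a row is the square.

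| True mean (mg/dl) | One check, CV 10 / 15 / 20% | Two checks in a row |
|---|---|---|
| 3.2 | 0.266 / 0.338 / 0.377 | 0.071 / 0.115 / 0.142 |
| 3.5 | 0.077 / 0.170 / 0.238 | 0.006 / 0.029 / 0.056 |
| 4.0 | 0.006 / 0.048 / 0.106 | 0.000 / 0.002 / 0.011 |

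A chance dip is therefore unlikely to persist across checks. It mostly causes delay, and losing a session mainly needs lasting improvement. Early values after embolisation may be worse than baseline (Table 1 in section 1.2 shows 9 of 37 comparable patients with reversible grade 3 bilirubin), which would lower these chances.

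**6. When the check is made.** Section 3.2 names a day-20 follow-up that neither schedule table lists. Section 7.1, however, calls for liver tests every 10 days in the first month, which implies one at day 20. Section 8.4.2 uses day 7±4 and the session day. Table 3's day-30 column is the next session day, since the DEB-TACE row is marked there, and it includes laboratory tests and an examination. So the sections do not agree on which reading decides.

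**The case against.** The strongest objection is about safety. A reader might infer from the laboratory rows that the re-check protects nobody and that inclusion 6 can simply be dropped after enrolment. The documents do not support that. Section 4.3 does not exclude severe ascites, and section 1.2 reports large ascites as a risk factor for procedure-related death or urgent transplant (p = 0.0002). A patient who qualified on ascites alone and worsens to severe is stopped by the present rule. So the block does not always reflect improvement, and the fix must carry its own ascites limit. This part of the objection stands in full.

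Second, the wording is soft: 4.2 says should, and 3.2 says if rather than only if. Clinicians may treat the rule as a ceiling on dysfunction. That is plausible in practice and makes it too strong to call every session given with no item left a certain deviation. But no section says inclusion 6 lapses after enrolment, and the stated discretion runs only to delaying, cancelling or stopping early.

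Third, limiting repeat sessions to patients who still have marginal reserve is a coherent choice for this trial. That is fair, but the plan does not say it is intended, and it does not say what then happens to planned lesions left untreated.

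Fourth, the effect is probably rare. A block by improvement needs all seven items absent after embolisation; thrombosis and shunts are structural and unlikely to clear; and section 7.1 expects up to half of patients to have a liver side effect. This stands. It would be wrong to read 27–38% as the share of patients blocked: it is one hypothetical patient at 3.2 mg/dl under assumed variation.

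A reader might also infer that the day-20 check has no basis in the plan. Section 7.1 supplies one. The problem is only that the sections are not aligned.

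**Conclusion.** The point holds as a minor one of wording. As written, 3.2 and 4.2 bar a multi-session patient with none of the seven items left from the next planned session for as long as that lasts. For laboratory items the bar adds only lower bounds to limits already in section 4.3; for ascites it gives partial protection worth keeping.

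At most 25 of 51 patients face a re-check, few are likely to be blocked, and the usual result is delay within about 60 days of slack. A lost session mainly needs improvement that lasts beyond that. These statements rest on sessions about 30 days apart and on the 8.3 and 8.4.2 limits; the bilirubin probabilities rest wholly on the assumptions stated with them.

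A reader might infer that the rule biases the primary response rate or weakens the design. The documents do not support this: the primary endpoint counts treated lesions, and sample size and error rates are unchanged.

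**What to change.** - In 3.2 and 4.2, state that the requirement to have at least one inclusion 6 item applies at enrolment only.
- Before each repeat session, keep all section 4.3 exclusions and the other inclusion criteria binding, and add that ascites must be no worse than moderate (no severe or refractory ascites, a category that Appendix 2 already uses).
- Make the day of the scheduled repeat session, as in 8.4.2 and Table 3, the deciding check for any interval up to the 90 days in 8.3. Align the day-20 follow-up in 3.2 and the 10-day laboratory checks in 7.1 with it.
- Leave physician discretion to delay or cancel as it is.

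The downside is that some repeat-session data will come from patients whose liver function has improved past the entry threshold. Record the inclusion 6 values before each session so that they can be identified. If the sponsor does want repeat sessions limited to patients still meeting inclusion 6, 3.2 should say so and state what happens to the untreated lesions.

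The cost is wording in 3.2, 4.2, 7.1 and 8.4.2 and a line or two on the re-treatment form. The laboratory tests and examination are already scheduled, so no new tests, visits or patients are needed.
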